#### 7.4.1.2 Censoring for time to event endpoints for interim and final analyses

Please refer to [Section 6.8](#) above.

#### 7.4.1.3 Testing hierarchy

In the  $i$ -th analysis,  $i=1, \dots, K$ , the upper limit of the two sided  $(1-2*\alpha_i)*100\%$  confidence interval of the hazard ratio will be compared with the non-inferiority margin of 1.3. Also the one-sided p-value of the non-inferiority test based on the Wald chi-squared statistic will be given. If the non-inferiority test is significant, i.e. non-inferiority within the margin of 1.3 has been demonstrated, a superiority test (Wald chi-squared statistic) will be performed. If the superiority test is significant, a superiority test on the first key secondary endpoint will be performed at the same significance level as used for the primary endpoint. If this superiority test is also significant, the second and third key secondary endpoints will be tested hierarchically. The second and third key secondary endpoints will be analysed with a Chi-Square test at the same significance level  $(2*\alpha_i)*100\%$  as the primary endpoint.

#### 7.4.1.4 Details on alpha-spending

The following details on alpha-spending will hold:

##### *a) Early stop of the study due to superiority or futility*

If the decision is to terminate the study after a formal DMC interim analysis due to superiority of linagliptin over glimepiride or futility, further endpoint events are expected to be documented before the study is stopped. These events will also be adjudicated and subsequently used for the final analysis.

The final, confirmatory analysis will be based on all (primary) endpoint events observed until study end. This analysis will be performed based on the same significance level  $\alpha_i$  as the interim analysis that led to early stopping of the trial.

*b) Early stop of the study due to safety reasons*

If the study is terminated prematurely (before observation of 631 patients with primary endpoint events) as a consequence of DMC safety reviews, the remaining significance level alpha will be fully exhausted at this step (taking into account previous official interim analysis), and the analysis will be based on all observed and confirmed (primary) endpoints events.

*c) Underrunning at study end (not stopping prematurely)*

If, for logistical reasons, the study is terminated with fewer than 631 patients with primary endpoint events, the remaining significance level alpha will be fully exhausted at this step (taking into account previous official interim analysis).

*d) Overrunning at study end (not stopping prematurely)*

If, for logistical reasons, the study is terminated with more than 631 patients with primary endpoint events, the significance level alpha as determined for 631 patients with primary endpoint events will be used (taking into account previous official interim analysis).

## **7.4.2 Sensitivity analysis**

### **7.4.2.1 Proportional hazards assumption violated**

In case the proportionality assumption is violated, an attempt will be undertaken to identify groups of patients for which the proportionality assumption holds and a stratified log-rank test will be performed. The HR and corresponding CI will be obtained from the stratified Cox model.

In addition a piecewise Cox model assuming proportional hazards in a series of consecutive time intervals as proposed by Collett (7) will be investigated.

### **7.4.2.2 General sensitivity analysis**

For the primary endpoint sensitivity analyses will be done on the PPS, the OS and the TS population in combination with censoring on day 0 (TS+0) and on day 30 (TS+30). For all these analyses, the allocated trial treatment at randomisation will be used for treatment assignment.

Sensitivity analyses done on the PPS, OS population and on TS population in combination with censoring on day 30 will be performed based on events occurring within the time patients are on-treatment + 30 days after permanent treatment discontinuation or date of last documented study visit, whichever comes first.

This means patients will be considered censored at the date of last treatment stop + 30 days, if their last documented study visit was performed thereafter. If the last documented study visit was performed earlier than 30 days after last treatment stop, the patient will be censored at the last documented study visit (refer to [Section 6.8.3](#)).

The sensitivity analysis done on the TS in combination with censoring on day 0 will be based on events occurring within the time patients are on-treatment or date of the individual day of trial completion, whichever comes first.

These sensitivity analyses will be performed as described in [Section 7.4.1.1](#) at the significance level used for the primary analysis.

The following table provides an overview of the planned analyses.

Table 7.4.2.2: 1 Overview of analyses on the primary endpoint

Censoring mechanism	Analysis set		
	TS	PPS	OS
Individual day of trial completion	x		
0 days censoring	x		
7 days censoring	x		
30 days censoring	x	x	x

For the details on censoring refer to [Section 6.8.3](#).

For the primary endpoint an additional sensitivity analysis will be performed in addition on the TS considering all events that occurred between randomisation and 7 days after the last permanent treatment discontinuation or date of last documented study visit, whichever comes first. Accordingly, patients without an event will be considered censored at the earliest of the date of last treatment discontinuation + 7 days or last documented study visit.

The cumulative incidence for the time to first occurrence of the primary endpoint will be presented, accounting for the time to non-CV death as competing risk. In addition, a Cox's proportional hazards model will be fitted to compare the distribution of competing risks between treatment groups.

#### **7.4.4 Interim analysis**

The significance level  $\alpha$  is determined as described in [Section 7.4.1](#). For the interim analysis patients without events will be considered censored as described in [Section 7.4.1.2](#).

The DMC will perform formal interim analyses as outlined in the DMC charter. A separate Statistical Analysis Plan for the interim analysis will be provided. The transfer of data is outlined in the Interim Analysis Logistics Plan (logistical aspects), as well as the Data Transmission Agreement signed by the DMC Statistician.

### **7.5 SECONDARY ENDPOINTS**

#### **7.5.1 Key secondary endpoints**

##### *Primary analysis of key secondary endpoints*

The first key secondary endpoint of time to first 4P-MACE will be analysed on the TS as described in [Section 7.4.1](#), at the same significance level  $\alpha_i$  as the primary endpoint.

The second and third composite key secondary endpoints will be analysed with a Chi-Square test at the same significance level  $\alpha_i$  as the primary endpoint, based on the TS.

The number and percentage of patients with response will be provided along with the 95% Wilson confidence intervals.

A logistic regression model will be applied including a term for 'treatment'. The Odds ratio

(OR) along with the  $(1-2*\alpha_i)*100\%$  Wald CI and the two-sided p-value for treatment comparison will be presented.

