**Proprietary confidential information.**

© 2019 Boehringer Ingelheim International GmbH or one or more of its affiliated companies. All rights reserved.

This document may not - in full or in part - be passed on, reproduced, published or otherwise used without prior written permission.

If the superiority hypothesis has revealed a significant result, then fourthly the second key secondary endpoint will be analysed hierarchically. The second key secondary endpoint (see Section 7.1) will be tested regarding the following hypothesis (p: probability for composite endpoint)

$H_{0(\text{key secondary } 2)}: p_{\text{linagliptin}} - p_{\text{glimepiride}} = 0$  vs.

( $H_{0(\text{key secondary } 2)}$ : Linagliptin is equal to glimepiride regarding the occurrence of the second key secondary endpoint.)

$H_{1(\text{key secondary } 2)}: p_{\text{linagliptin}} - p_{\text{glimepiride}} \neq 0$

( $H_{1(\text{key secondary } 2)}$ : Linagliptin is unequal to glimepiride regarding the occurrence of the second key secondary endpoint.)

If this hypothesis has revealed a significant result, then fifthly the third key secondary endpoint will be tested hierarchically regarding the following hypothesis:

$H_{0(\text{key secondary } 3)}: p_{\text{linagliptin}} - p_{\text{glimepiride}} = 0$  vs.

( $H_{0(\text{key secondary } 3)}$ : Linagliptin is equal to glimepiride regarding the occurrence of the third key secondary endpoint.)

$H_{1(\text{key secondary } 3)}: p_{\text{linagliptin}} - p_{\text{glimepiride}} \neq 0$

( $H_{1(\text{key secondary } 3)}$ : Linagliptin is unequal to glimepiride regarding the occurrence of the third key secondary endpoint.)

Any confirmatory hypothesis test will be performed on the full analysis set.

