### 7.3.1 Primary analyses

The one-sided overall significance level will be  $\alpha=2.5\%$ . For the primary analysis a 'classical ITT-analysis on the FAS will be performed as described above.

For the primary analysis a cox proportional hazards regression model of time to the first event with factor treatment will be conducted. The non-inferiority margin will be 1.3.

As described in Section [7.3.4](#) the DMC will perform formal interim analyses. The overall significance level of 2.5% will be allocated to the DMC-interim analyses and the final analysis according to the O'Brien & Fleming alpha-spending function. The O'Brien & Fleming alpha-spending function defined the significance level for the first interim analysis on 4P-MACE.

Due to the change of the primary endpoint after the first DMC interim analysis a Bonferroni adjustment will be applied in addition, to control the overall alpha-level. That means, the alpha spent at the first DMC interim analysis (performed for 4P-MACE and based on the O'Brien & Fleming alpha-spending function) is subtracted from the initial overall alpha. The O'Brien & Fleming alpha-spending function based on the new overall alpha (after additional Bonferroni adjustment) defines the allocation of the still available overall significance level for the second interim analysis and the final analysis.

The significance levels for the analyses are denoted by  $\alpha_i$ ,  $i=1,\dots,3$ . The total number of analyses is three, including 2 interim analyses.

In the  $i$ -th analysis,  $i=1,\dots,3$ , the upper limit of the two sided  $(1-2*\alpha_i)*100\%$ -confidence interval of the hazard ratio will be compared with the non-inferiority margin. Also the one-sided p-value of the non-inferiority test based on the Wald chi-squared statistic will be given. If the non-inferiority test satisfies the non-inferiority margin, a superiority test (Wald chi-squared statistic) will be performed. If the superiority test has revealed a significant result, a superiority test on the first key secondary endpoint will be performed on the same significance level as for the primary endpoint. If the superiority test has revealed a significant result, the second and third key secondary endpoints will be tested hierarchically (see Section [7.2](#)). The second and third key secondary endpoints will be analysed with Chi-Square test on the same significance level  $(2*\alpha_i)*100\%$  as the primary endpoint.

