### **7.4 PRIMARY ENDPOINT**

#### **7.4.1 Primary analysis**

For the primary endpoint of time to the first occurrence of any of the following CEC confirmed adjudicated components of the primary composite endpoint: CV death (including

fatal stroke and fatal MI), non-fatal MI (excluding silent MI), or non-fatal stroke an ITT-analysis (as randomised) on the TS will be performed. The analysis will be performed on TS with patients considered as randomised (intention-to-treat) and all events up to individual day of trial completion considered.

The randomised study treatment will be used to assign patients and events to treatment groups; all adjudicated events which occur until study end will be taken into account (i.e. independent of whether or not a patient was still on study medication).

The time to the primary endpoint will be derived from the date of randomisation.

The one-sided overall significance level will be  $\alpha=2.5\%$ . As described in the CTP, the DMC will perform formal interim analyses. The significance levels for the analyses are denoted by  $\alpha_i$ ,  $i=1, \dots, K$ , where K is the total number of analyses.

The O'Brien & Fleming alpha-spending function defined the significance level for the first interim analysis on 4P-MACE.

Due to the change of the primary endpoint after the first DMC interim analysis a Bonferroni adjustment will be applied in addition, to control the overall alpha level.

That means, the alpha spent at the first DMC interim analysis (performed for 4P-MACE and based on the O'Brien & Fleming alpha-spending function) is subtracted from the initial overall alpha. The O'Brien & Fleming alpha spending function based on the new overall alpha (after additional Bonferroni adjustment) defines the allocation of the still available overall significance level for the second interim analysis and the final analysis.

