#### *Sensitivity analysis of key secondary endpoints*

For the first key secondary endpoint of time to first 4P-MACE sensitivity analyses will be done on the PPS, the OS and TS+0, TS+30.

These sensitivity analyses will be performed based on events occurring within the time patients are on-treatment + 30 days after permanent treatment discontinuation or date of last documented study visit, whichever comes first.

For further details refer to [Section 7.4.2](#).

For the time to first 4P-MACE an additional sensitivity analysis will be performed on the TS considering all events that occurred between randomisation and 7 days after the last permanent treatment discontinuation or date of last documented study visit, whichever comes first. Accordingly, patients without an event will be considered censored at the earliest of the date of last treatment discontinuation + 7 days or last documented study visit.

The cumulative incidence for the time to first 4P-MACE will be presented, accounting for the time to non-CV death as competing risk. In addition, a Cox's proportional hazards model will be fitted to compare the distribution of competing risks between treatment groups.

For the second and third key secondary endpoints sensitivity analyses will be done on the PPS and the 30-days-treatment set OS, including the same statistical procedures as described above for the TS.

For the sensitivity analysis on the PPS patients who prematurely discontinue study treatment will be counted as non-responders as in the primary analysis on the TS.

For the sensitivity analysis on the 30-days-treatment set patients who prematurely discontinue study treatment will not necessarily be counted as non-responders. The measurement of the last documented on-treatment study visit will be used in this case.

The significance level from the primary analysis of key secondary endpoints will be used.

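### SAP 7.5.1 tests the second and third key secondary endpoints, which are two-sided, at the one-sided level alpha_i; protocol 7.3.1 and SAP 7.4.1.3 use 2*alpha_i.

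*SAP*

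**What the plan says.** - **What alpha_i is.** SAP 7.4.1 introduces it with "The one-sided overall significance level will be" 2.5%, and each alpha_i is one analysis's share of that. Protocol 7.3.1 does the same. Both documents judge the primary endpoint with a two-sided (1-2*alpha_i)*100% confidence interval.
- **Hypotheses.** Protocol 7.2 gives key secondary endpoints 2 and 3 a null of zero difference in proportions and a two-sided alternative: "Linagliptin is unequal to glimepiride regarding the occurrence of the second key secondary endpoint". The third endpoint has the same form.
- **Protocol 7.3.1.** "The second and third key secondary endpoints will be analysed with Chi-Square test on the same significance level", and the level printed next is (2*alpha_i)*100%.
- **SAP 7.4.1.3 (Testing hierarchy).** "The second and third key secondary endpoints will be analysed with a Chi-Square test at the same significance level", again followed by (2*alpha_i)*100%.
- **SAP 7.5.1.** "The second and third composite key secondary endpoints will be analysed with a Chi-Square test at the same significance level", followed by alpha_i with no factor 2. The same subsection reports the odds ratio with a (1-2*alpha_i)*100% interval: "Wald CI and the two-sided p-value for treatment comparison will be presented".
- **Sensitivity analyses, end of SAP 7.5.1.** "The significance level from the primary analysis of key secondary endpoints will be used", so the per-protocol and on-treatment-set analyses take over whichever level 7.5.1 sets.

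**The concern.** A two-sided p-value compared with alpha_i faces a threshold half the size of the one in the protocol and in the SAP's own hierarchy section. A chi-square p-value between alpha_i and 2*alpha_i would pass step 4 under SAP 7.4.1.3. Under SAP 7.5.1 it would fail, and step 5 would be closed as well. The odds-ratio interval that 7.5.1 reports beside the failed test would normally exclude 1.

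SAP 7.5.1 is the section devoted to analysing these endpoints, so it is the one a programmer would work from. If the conflict came to light after unblinding, choosing a threshold would be a post hoc decision on a confirmatory claim.

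**Working it through.** **1. Is alpha_i one-sided?** Protocol 7.6 gives the inputs: 631 events, 1:1 allocation, alpha = 2.5%, power 90.9% for non-inferiority (HR 1.0, margin 1.3) and 80% for superiority (HR 0.8). Schoenfeld's formula is power = Φ(|ln r| × √d / 2 − z), where r is the margin or the HR, d = 631 and √631/2 = 12.56.

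| | 2.5% one-sided (z = 1.960) | 2.5% two-sided (z = 2.241) | Protocol |
|---|---|---|---|
| Non-inferiority, r = 1.3 | 90.9% | 85.4% | 90.9% |
| Superiority, r = 0.8 | 80.0% | 71.3% | 80% |

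Only the one-sided reading reproduces the protocol's figures. So alpha_i is a one-sided level, and the equivalent level for a two-sided p-value is 2*alpha_i.

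**2. Size of alpha_i.** The documents do not print it. Assumptions:
- O'Brien-Fleming-type spending, a(t) = 2 × [1 − Φ(z(1−a/2)/√t)], with a = 0.025 one-sided.
- The alpha spent at the first look is subtracted, as SAP 7.4.1 describes.
- Looks at 411 and 631 events (protocol 7.3.4).
- A first look anywhere from 80 events (the minimum in protocol 7.3.4) to 190 (the figure in the protocol's modification summary).

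| Quantity | First look at 80 | First look at 190 |
|---|---|---|
| alpha_1 = a(d1/631) | 3.1e-10 | 4.4e-5 |
| Remaining a' = 0.025 − alpha_1 | 0.025000 | 0.024956 |
| alpha_2, at t = 411/631 = 0.651 with a' | 0.00548 | 0.00547 |
| alpha_3 | 0.02330 | 0.02326 |
| 2*alpha_2 | 0.01096 | 0.01094 |
| 2*alpha_3 | 0.04660 | 0.04652 |

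Here alpha_3 = 1 − Φ(c3), and c3 solves P(Z2 < c2, Z3 < c3) = 1 − a' with c2 = z(1 − alpha_2) and correlation √0.651. The timing of the first look hardly matters.

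**3. The two rules compared.**

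| | Protocol 7.3.1 and SAP 7.4.1.3 (2*alpha_i) | SAP 7.5.1 (alpha_i) |
|---|---|---|
| Final analysis, two-sided p | < 0.0465 to 0.0466 | < 0.0233 |
| Final analysis, \|z\| | > 1.99 | > 2.27 |
| Matching confidence interval | about 95.3% | about 97.7% |
| Final analysis after an early stop at the second interim | p < 0.0109 to 0.0110 | p < 0.0055 |

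The last row follows from SAP 7.4.1.4(a), which for that case says "This analysis will be performed based on the same significance level" as the interim that stopped the trial. The interval that 7.5.1 reports is the 95.3% one, so it matches the 2*alpha_i test and not the test 7.5.1 prints.

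**4. Cost in power.** With alpha_3 = 0.02326, an effect with 80% power at 2*alpha_3 has Φ(z(0.80) + z(1−alpha_3) − z(1−alpha_3/2)) = Φ(0.842 + 1.991 − 2.269), about 71%, at alpha_3. An effect with 90% power drops to about 84%. A two-sided p of 0.03 passes under SAP 7.4.1.3 and fails under 7.5.1.

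**The case against.** The strongest reply is that 7.5.1 ties the level to that of the primary endpoint. Because the primary alpha_i is one-sided, this can be read as a loose way of writing two-sided 2*alpha_i. The interval beside it points the same way, SAP 7.4.1.3 and the protocol state the rule explicitly, and the SAP says that it rests on the protocol's statistical section. On this view the line is a notation slip, and a real dispute at analysis is unlikely.

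That establishes the intent but does not make the line right. The sentence prints alpha_i for a test with a two-sided p-value, while two near-identical sentences elsewhere print the factor 2. Just before it, 7.5.1 uses alpha_i correctly for 4P-MACE, which is a one-sided superiority test, so the symbol was probably carried over. The SAP's list of changes, as provided, shows no deliberate change to this level.

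Several limits do stand:
- The literal reading is conservative and inflates no type I error.
- It matters only after non-inferiority, 3P-MACE superiority and 4P-MACE superiority have all succeeded.
- Both endpoints depend on status at study end or the final visit, so the alpha_2 threshold is relevant mainly to a final analysis after an early stop.
- The chi-square test and the logistic Wald interval nearly always agree but are not identical.

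**Conclusion.** The concern holds. SAP 7.5.1 as written sets the wrong decision threshold for steps 4 and 5. It contradicts protocol 7.3.1, SAP 7.4.1.3 and its own confidence interval by a factor of two, and that factor depends on no assumption. The specific thresholds do: they rest on the assumed O'Brien-Fleming-type spending and on the look timings listed above, because no alpha_i is printed. The weight of the text shows that 2*alpha_i is the prespecified rule, so 7.5.1 is the line to correct. This should be fixed, but it does not threaten the primary conclusion.

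**What to change.** In SAP 7.5.1, state that the two-sided chi-square p-value for the second and third key secondary endpoints is compared with 2*alpha_i, as in protocol 7.3.1 and SAP 7.4.1.3. Leave alpha_i in place for the one-sided 4P-MACE test. For these two endpoints, let the closing sentence on sensitivity analyses refer to the corrected two-sided level. The cost is one line of SAP wording, made before unblinding. No design element changes, no extra alpha is spent, and the protocol needs no amendment.

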#### General definition of second and third key secondary endpoints

If a patient has terminated study treatment permanently (i.e. without subsequent re-start) before trial stop, the patient is considered a non-responder (except in sensitivity analyses). A patient who stops study treatment and restarts later, can still fulfill the second and third composite key secondary endpoint criteria, independent from how long the patient was off-drug. Only the last information on 'termination of trial medication' (i.e. last treatment stop date) is considered.

If a patient died prior to completing the trial regularly, the patient is considered as non-responder.

HbA1c and weight and hypoglycaemia are only considered for the (parameter-specific) time on-treatment and not e.g. at/until a follow-up visit, because the follow-up visit is planned to be performed after treatment discontinuation.

#### *Sensitivity analysis of key secondary endpoints*

For the first key secondary endpoint of time to first 4P-MACE sensitivity analyses will be done on the PPS, the OS and TS+0, TS+30.

These sensitivity analyses will be performed based on events occurring within the time patients are on-treatment + 30 days after permanent treatment discontinuation or date of last documented study visit, whichever comes first.

For further details refer to [Section 7.4.2](#).

For the time to first 4P-MACE an additional sensitivity analysis will be performed on the TS considering all events that occurred between randomisation and 7 days after the last permanent treatment discontinuation or date of last documented study visit, whichever comes first. Accordingly, patients without an event will be considered censored at the earliest of the date of last treatment discontinuation + 7 days or last documented study visit.

The cumulative incidence for the time to first 4P-MACE will be presented, accounting for the time to non-CV death as competing risk. In addition, a Cox's proportional hazards model will be fitted to compare the distribution of competing risks between treatment groups.

For the second and third key secondary endpoints sensitivity analyses will be done on the PPS and the 30-days-treatment set OS, including the same statistical procedures as described above for the TS.

For the sensitivity analysis on the PPS patients who prematurely discontinue study treatment will be counted as non-responders as in the primary analysis on the TS.

For the sensitivity analysis on the 30-days-treatment set patients who prematurely discontinue study treatment will not necessarily be counted as non-responders. The measurement of the last documented on-treatment study visit will be used in this case.

The significance level from the primary analysis of key secondary endpoints will be used.

